5.3 METHODS AND TIMING FOR CAPTURING AND ASSESSING SAFETY PARAMETERS

The investigator is responsible for ensuring that all adverse events (see Section 5.2.1 for definition) are recorded on the adverse event eCRF and reported to the Sponsor in accordance with instructions provided in this section and in Sections 5.4-5.6.

For each adverse event recorded on the adverse event eCRF, the investigator will make an assessment of seriousness (see Section 5.2.2 for seriousness criteria), severity (see Section 5.3.3), and causality (see Section 5.3.4).

5.3.1 Adverse Event Reporting Period

Investigators will seek information on adverse events at each patient contact. All adverse events, whether reported by the patient or noted by study personnel, will be recorded in the patient's medical record and on the adverse event eCRF.

After informed consent has been obtained but prior to initiation of GDC-8264, *all* serious adverse events should be reported (see Section 5.4.2 for instructions for reporting serious adverse events).

After initiation of GDC-8264, all adverse events will be reported until after the final dose of GDC-8264.

Instructions for reporting adverse events that occur after the adverse event reporting period are provided in Section 5.6.

GDC-8264—Genentech, Inc. 77/Protocol GA43861, Version 4

5.3.2 Eliciting Adverse Event Information

A consistent methodology of non-directive questioning should be adopted for eliciting adverse event information at all patient evaluation timepoints. Examples of nondirective questions include the following:

"How have you felt since your last clinic visit?"

"Have you had any new or changed health problems since you were last here?"

5.3.3 Assessment of Severity of Adverse Events

The investigator will use the NCI CTCAE (v5.0) grading scale for assessing the severity of each adverse event reported during the study. The investigator will use the grading scale in Table 8 for assessing the severity of adverse events that are not specifically listed in NCI CTCAE.

For infection adverse events, the investigator will also use the Blood and Marrow Transplant Clinical Trial Network (BMT CTN) infection severity grading system (see Appendix 7) for assessing the severity of infection adverse events (i.e., in addition to using the NCI CTCAE grading scale).

Table 8 Adverse Event Severity Grading Scale for Events Not Specifically Listed in NCI CTCAE

Grade	Severity
1	Mild; asymptomatic or mild symptoms; clinical or diagnostic observations only; or intervention not indicated
2	Moderate; minimal, local, or non-invasive intervention indicated; or limiting age-appropriate instrumental activities of daily living ^a
3	Severe or medically significant, but not immediately life-threatening; hospitalization or prolongation of hospitalization indicated; disabling; or limiting self-care activities of daily living ^{b, c}
4	Life-threatening consequences or urgent intervention indicated ^d
5	Death related to adverse event ^d

NCI CTCAE = National Cancer Institute Common Terminology Criteria for Adverse Events. Note: Based on the most recent version of NCI CTCAE (v5.0), which can be found at: http://ctep.cancer.gov/protocolDevelopment/electronic_applications/ctc.htm

- ^a Instrumental activities of daily living refer to preparing meals, shopping for groceries or clothes, using the telephone, managing money, etc.
- ^b Examples of self-care activities of daily living include bathing, dressing and undressing, feeding oneself, using the toilet, and taking medications, as performed by patients who are not bedridden.
- ^c If an event is assessed as a "significant medical event," it must be reported as a serious adverse event (see Section 5.4.2 for reporting instructions), per the definition of serious adverse event in Section 5.2.2.
- ^d Grade 4 and 5 events must be reported as serious adverse events (see Section 5.4.2 for reporting instructions), per the definition of serious adverse event in Section 5.2.2.

5.3.4 Assessment of Causality of Adverse Events

Investigators should use their knowledge of the patient, the circumstances surrounding the event, and an evaluation of any potential alternative causes to determine whether an adverse event is considered to be related to the GDC-8264, indicating "yes" or "no" accordingly. The following guidance should be taken into consideration (see also Table 9):

- Temporal relationship of event onset to the initiation of GDC-8264
- Course of the event, with special consideration of the effects of dose reduction, discontinuation of GDC-8264, or reintroduction of GDC-8264 (as applicable)
- Known association of the event with GDC-8264 or with similar treatments
- Known association of the event with the disease under study
- Presence of risk factors in the patient or use of concomitant medications known to increase the occurrence of the event
- Presence of non–GDC-8264–related factors that are known to be associated with the occurrence of the event (e.g., adverse events associated with standard-of-care treatment with systemic corticosteroids or medications commonly used in the management of aGVHD)

Table 9 Causal Attribution Guidance

Is the adverse event suspected to be caused by the study drug on the basis of facts, evidence, science-based rationales, and clinical judgment?

- YES There is a plausible temporal relationship between the onset of the adverse event and administration of the study drug, and the adverse event cannot be readily explained by the patient's clinical state, intercurrent illness, or concomitant therapies; and/or the adverse event follows a known pattern of response to the study drug; and/or the adverse event abates or resolves upon discontinuation of the study drug or dose reduction and, if applicable, reappears upon rechallenge.
- NO An adverse event will be considered related, unless it fulfills the criteria specified below. Evidence exists that the adverse event has an etiology other than the study drug (e.g., preexisting medical condition, underlying disease, intercurrent illness, or concomitant medication); and/or the adverse event has no plausible temporal relationship to administration of the study drug (e.g., cancer diagnosed 2 days after first dose of study drug).

5.3.5 Procedures for Recording Adverse Events

Investigators should use correct medical terminology/concepts when recording adverse events on the adverse event eCRF. Avoid colloquialisms and abbreviations.

Only one adverse event term should be recorded in the event field on the adverse event eCRF.

5.3.5.1 Diagnosis versus Signs and Symptoms

A diagnosis (if known) should be recorded on the adverse event eCRF rather than individual signs and symptoms (e.g., record only liver failure or hepatitis rather than jaundice, asterixis, and elevated transaminases). However, if a constellation of signs and/or symptoms cannot be medically characterized as a single diagnosis or syndrome at the time of reporting, each individual event should be recorded on the adverse event eCRF. If a diagnosis is subsequently established, all previously reported adverse events based on signs and symptoms should be nullified and replaced by one adverse event report based on the single diagnosis, with a starting date that corresponds to the starting date of the first symptom of the eventual diagnosis.

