2. OBJECTIVES AND ENDPOINTS

This study will evaluate the safety, pharmacokinetics, and efficacy of GDC-8264 given in combination with standard-of-care corticosteroid treatment in patients with high-risk aGVHD. The overall purpose of the study is to identify an optimal dose for GDC-8264 for future studies, using all available safety, PK, and efficacy data. Specific objectives and corresponding endpoints for the study are outlined below.

In this protocol, "study drug" refers to GDC-8264; "study treatment" refers to the combination of treatments assigned to patients as part of this study (i.e., GDC-8264 and corticosteroids).

GDC-8264—Genentech, Inc. 32/Protocol GA43861, Version 4

Co-Primary Objectives	Corresponding Endpoint
 To evaluate the safety of GDC-8264 	 Incidence and severity of adverse events, with severity determined according to the NCI CTCAE v5.0 grading scale
To characterize the pharmacokinetics of GDC-8264	 Plasma concentration of GDC-8264 at specified timepoints, and relevant PK parameters
Secondary Objectives	Corresponding Endpoints
 To evaluate the efficacy of GDC-8264 	 ORR, defined as the proportion of patients with a CR, VGPR, or PR on Day 29 with no intervening additional line of aGVHD therapy, as determined by the investigator ^a
	 DOR, defined as the time from response (CR, VGPR or PR) on Day 29 to aGVHD progression from nadir in any organ, new systemic therapy for aGVHD, or death from any cause (whichever occurs first), as determined by the investigator ^a
	Cumulative incidence of aGVHD flares by Day 56
	 Cumulative incidence of NRM by Day 180

Table 1 Objectives and Corresponding Endpoints

aGVHD=acute graft-versus-host disease; BMT CTN=Blood and Marrow Transplant Clinical Trials Network; CR=complete response; DOR=duration of response; FFS=failure-free survival; MAP=Mount Sinai Acute GVHD International Consortium [MAGIC] algorithm probability; NCI CTCAE=National Cancer Institute Common Terminology Criteria for Adverse Events v5.0; NRM=non-relapse mortality; ORR=overall response rate; OS=overall survival; PK=pharmacokinetic; PR=partial response; VGPR=very good partial response.

- ^a Responses are determined by the investigator. See Section 3.1.4 for key definitions and details on response criteria.
- ^b Baseline defined as last value prior to initiation of GDC-8264.

Exploratory Objectives	Corresponding Endpoints

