5.1.1 Potential Risks Associated with GDC-8264

5.1.1.1 Serious Bacterial or Viral Infections with Blunted Clinical Response

Mice that are homozygous for a knock-in mutation of RIP1 that inhibits kinase activity (i.e., KD mice) are viable, healthy, and born in Mendelian ratios (Newton et al. 2014). RIP1 inactivation or inhibition does not affect RIP1 stability and also does not affect TNF-induced nuclear factor–kappa B or MAPK activation (Newton et al. 2014; Patel et al. 2020). When challenged with certain pathogens, such as vaccinia virus, some published reports suggest that RIP1 KD mice exhibit impaired pathogen clearance and can therefore manifest more severe infections compared with WT controls (Polykratis et al. 2014, Shutinoski et al. 2016). However, other studies conducted under similar experimental conditions have failed to reproduce these results (Kuriakose et al. 2016,

GDC-8264—Genentech, Inc. 69/Protocol GA43861, Version 4 Zhang et al. 2020). Similarly, infection with murine gamma herpes virus MHV68 showed no significant differences in levels of MHV68 in lungs or spleens or changes in leukocyte populations between RIP1 KD and WT mice (Webster et al. 2020). In addition, RIP1 inactivation does not affect cellular nuclear envelope rupture (a critical step for viral replication) or proinflammatory cytokine production during influenza A–virus infection (Kuriakose et al. 2016). However, considering the uncertainty of the translatability of some of these reported findings to humans, the Sponsor cannot exclude the potential risk that inhibition of RIP1 with GDC-8264 could increase the risk of serious infections.

RIP1 KD mice may demonstrate a blunted systemic inflammatory response to certain inflammatory stimuli. For example, in WT mice, TNF causes hypothermia (a manifestation of severe systemic inflammation) and shock; however, hypothermia and shock do not occur after TNF administration to RIP1 KD mice (Newton et al. 2014). Also, it has been reported that RIP1 KD mice may be impaired in their inflammatory response to lipopolysaccharide, although other published data have not replicated this finding (Newton et al. 2016, Saleh et al. 2017). Nevertheless, if this result translates to humans, it is possible that patients exposed to GDC-8264 who have active infections may exhibit a blunted clinical response. As such, patients with uncontrolled active infections are excluded from this study (see Section 4.1.2).

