5.3.5.3 Persistent or Recurrent Adverse Events

A persistent adverse event is one that extends continuously, without resolution, between patient evaluation timepoints. Such events should only be recorded once on the adverse event eCRF. The initial severity (intensity or grade) of the event will be recorded at the time the event is first reported. If a persistent adverse event becomes more severe, the most extreme severity should also be recorded on the adverse event eCRF. If the event becomes serious, it should be reported to the Sponsor immediately (i.e., no more than 24 hours after learning that the event became serious; see Section 5.4.2 for reporting instructions). The adverse event eCRF should be updated by changing the event from "non-serious" to "serious," providing the date that the event became serious, and completing all data fields related to serious adverse events.

A recurrent adverse event is one that resolves between patient evaluation timepoints and subsequently recurs. Each recurrence of an adverse event should be recorded as a separate event on the adverse event eCRF. Investigators should use clinical judgment to assess each event as recurrent or intermittent. An intermittent adverse event should be recorded as a single event.

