5.3.5.8 Preexisting Medical Conditions

A preexisting medical condition is one that is present at the screening visit for this study. Such conditions should be recorded on the eCRF.

A preexisting medical condition should be recorded as an adverse event only if the frequency, severity, or character of the condition worsens during the study. When recording such events on the adverse event eCRF, it is important to convey the concept that the preexisting condition has changed by including applicable descriptors (e.g., "more frequent headaches").

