6.4 SAFETY ANALYSES

The safety analysis population will consist of all patients who received at least one dose of GDC-8264, with patients grouped according to treatment received.

Safety will be assessed through descriptive summaries of exposure to study treatment (such as treatment duration, total dose received, and dose modifications), adverse events, changes in laboratory test results, and changes in ECGs and vital signs. All adverse event data will be listed by patient number.

All verbatim adverse event terms will be mapped to Medical Dictionary for Regulatory Activities thesaurus terms, and adverse event severity will be graded according to the NCI CTCAE v5.0. In addition, infection adverse event severity will be graded according to the BMT CTN Severity Grading Table (see Appendix 7). All adverse events, serious adverse events, adverse events leading to death, adverse events of special interest, and adverse events leading to study treatment discontinuation that occur on or after the first dose of study treatment (i.e., treatment-emergent adverse events) will be summarized by mapped term, appropriate thesaurus level, and severity grade. For events of varying

GDC-8264—Genentech, Inc. 91/Protocol GA43861, Version 4 severity, the highest grade will be used in the summaries. Deaths and cause of death will be summarized.

Relevant laboratory, vital sign (pulse rate, respiratory rate, blood pressure, and temperature), and ECG data will be displayed by time, with grades identified where appropriate. Additionally, a shift table of selected laboratory tests will be used to summarize the baseline and maximum postbaseline severity grade. Changes in vital signs and ECGs will be summarized.

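### Section 6.4 has no worsening clause, so a serious event reported before Day 1 that worsens on GDC-8264 can fall outside the treatment-emergent summaries

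*Combined protocol and SAP*

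**What the plan says.** - **Section 6.4.** AEs, SAEs, fatal AEs, AEs of special interest and AEs leading to treatment discontinuation "that occur on or after the first dose of study treatment (i.e., treatment-emergent adverse events) will be summarized by mapped term", as well as by thesaurus level and grade. Where severity varies, the highest grade is tabulated. The by-patient AE listing and the summary of deaths carry no such restriction.
- **Section 2.** Study treatment "refers to the combination of treatments assigned to patients as part of this study (i.e., GDC-8264 and corticosteroids", whereas study drug means GDC-8264 alone. Under 4.1.1 corticosteroids normally start on Day 1 or up to 3 days earlier.
- **Section 5.3.5.3.** On persistent events: "Such events should only be recorded once on the adverse event eCRF". On worsening: "If a persistent adverse event becomes more severe, the most extreme severity should also be recorded on the adverse event eCRF". A date is requested when a non-serious event turns serious, but not when the grade rises.
- **Section 5.3.5.1.** When a diagnosis is reached later, the symptom reports are nullified and replaced by a single report "with a starting date that corresponds to the starting date of the first symptom of the eventual diagnosis".
- **Sections 5.3.1 and 5.4.2.1.** Between consent and the first GDC-8264 dose every SAE is reported. Significant non-serious events go to medical history.
- **Section 5.3.5.8.** A condition present at the screening visit becomes an AE only if its frequency, "severity, or character of the condition worsens during the study". No start date is specified for that AE.

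**The concern.** AE incidence and severity is a co-primary endpoint (Table 1), and the two dose cohorts will be described largely through the 6.4 summaries. The first potential risk discussed in 5.1.1 is serious infection. Section 5.1.1.1 cites some published reports that RIP1 kinase-dead mice "exhibit impaired pathogen clearance and can therefore manifest more severe infections compared with WT controls". It adds that other studies did not reproduce this, and that the risk nevertheless cannot be excluded.

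An infection already present at the first dose that becomes more severe on GDC-8264 is the pattern this risk would produce. If the recording rules fix its onset before dosing, and the tabulation rule looks only at when the event occurred, the pattern can be missing from the summaries meant to show it.

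**Working it through.** The plan states no figure on this point, and 6.1 says that the sample size is not power-based, so there is nothing to reproduce. The check is to follow each type of event through the rules, taking occurring in 6.4 to mean onset.

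**Case A: SAE before Day 1 that worsens on drug.** An infection arises after the screening visit, is reported as an SAE before Day 1, persists, and goes from Grade 3 to Grade 4 on Day 8 (illustrative values).
1. 5.3.1 creates an AE record with an onset before dosing.
2. 5.3.5.3 adds Grade 4 to the same record. The event was already serious, so the became-serious date is not triggered, and no other date of worsening is requested.
3. 5.3.5.8 does not literally apply, because the condition was not present at the screening visit.
4. 6.4 excludes the record, because its onset precedes the first GDC-8264 dose and there is no worsening clause.

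**Case B: first symptom before Day 1, infection diagnosed and worsening on drug.** Persistent fever with no other sign or symptom does not bar entry (4.1.2). Suppose that further symptoms are recorded as AEs on drug and an infection is then diagnosed. Under 5.3.5.1 the symptom AEs are nullified and the diagnosis can take the date of the fever; no exception is made for a first symptom before dosing. 6.4 then excludes it. If the fever sits only in medical history and no symptom AE was reported on drug, there is nothing to nullify and the back-dating rule applies less clearly.

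**Case C: non-serious condition before dosing that worsens on drug.** It starts as medical history (5.4.2.1). The worsening is then an AE under 4.5.3, 5.2.1 or 5.3.5.8. It is counted if dated at the worsening, but no passage says which date applies.

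**Case D: event that begins between the first corticosteroid dose and Day 1.** If the first dose in 6.4 is the corticosteroid dose, the event is counted and Cases A and B narrow. Two problems remain. An event that began before the first corticosteroid dose and worsens on GDC-8264 is still excluded. An event that began and peaked before any GDC-8264 is counted as treatment-emergent.

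**Size of one case.** With about 20 patients per cohort (6.1), one patient is 1/20 = 5 percentage points. If 1, 2 or 3 patients in a cohort were affected (an assumption; the documents give no count), up to 5, 10 or 15 points would be missing from an event-specific incidence. The loss in overall AE incidence would be smaller, because a patient with another AE that starts on drug is still counted.

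**The case against.** **Worsening is mostly captured already.** Sections 4.5.3, 5.2.1 and 5.3.5.8 make worsening after the first dose an AE. Section 5.3.5.8 sets no severity limit, so a serious infection present at the screening visit falls under it too. Section 5.3.5.2 can give a severe or serious secondary event its own record. This stands. It confines the one-record problem to SAEs already on record before the first dose that worsen without a separately recorded secondary event. A reader might infer that any infection worsening on drug is lost; the documents do not support that.

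**An onset before dosing cannot be caused by the drug.** This also stands for an infection that is only diagnosed on drug and does not worsen. Leaving it out of a treatment-emergent table is defensible.

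**The cases are not hidden.** They remain in the AE listing and, if fatal, in the death summary. Reasons for treatment discontinuation are summarized separately (6.2), the Data and Safety Monitoring Board reviews all available safety data (3.1.3), and the exploratory infection endpoint in Table 1 is not expressly limited to treatment-emergent events. Infections are not AEs of special interest either, apart from suspected transmission through contaminated drug (5.2.3). A reader might infer that patient oversight fails; it does not. The defect lies in the summary tables.

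**Detail is deferred.** Section 6 leaves detailed specifications to the Data Analysis Plan, which is not among the documents and may add a worsening clause. That answers only part of the point: 6.4 itself defines the term, and a later plan cannot recover a date of worsening that was never collected.

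**A tempting count.** A reader might take the 64.7% infected through Day 56 cited in 1.1, derive a daily hazard of -ln(1 - 0.647)/56 = 0.0186, and assume 2 to 5 days from first symptom to diagnosis. That gives 0.0186 × 2 × 20 = 0.74 to 0.0186 × 5 × 20 = 1.86 infections per cohort. The documents do not support this as an estimate of what is lost:
- The lag is invented.
- The 64.7% was measured after high-dose corticosteroids began, whereas these normally start no more than 3 days before Day 1.
- The figure counts late diagnosis, not worsening.
- It ignores patients who have another infection on drug, and the corticosteroid-start reading of 6.4.

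**Conclusion.** The point holds in a narrow form. As written, 6.4 has no worsening clause and an unclear reference dose. Together with the one-record rule, it can leave an SAE that began before Day 1 and worsened on GDC-8264 out of the treatment-emergent AE and SAE summaries. The back-dating rule can do the same to an infection with an earlier first symptom that is diagnosed and worsens on drug. For non-serious conditions the gap is only the missing start-date rule.

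This rests on reading occurring as onset and on the Data Analysis Plan not saying otherwise. The number of affected patients is unknown. The point is still worth correcting, because it touches a co-primary endpoint and a named risk, each patient weighs 5 points in a cohort, and the missing date has to be collected during the study.

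**What to change.** 1. In 6.4, define treatment-emergent as any AE with onset on or after the first dose of GDC-8264, or any AE that began earlier and increases in grade or becomes serious on or after that dose. Naming GDC-8264 settles the reference date.
2. In 5.3.5.3 and on the AE eCRF, collect the date of worsening, or open a new record when an event ongoing at the first dose worsens.
3. State that an AE recorded under 5.3.5.8 is dated at the worsening.
4. Flag events whose first symptom preceded dosing and which were diagnosed on drug, and show them in a supplementary summary. Do not add first diagnosis to the main definition.
5. Carry the same definition into the Data Analysis Plan.

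**Cost:** one definition, one extra date field, a flag and a short eCRF completion note. The displayed AE rates may become slightly less favourable.
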